##### 11.3.2.2 Change in GALT HIV reservoirs

Change in GALT HIV reservoirs in rectal tissue from Baseline to Day 28 and Day 56 in HIV-infected subjects (Cohort 1) and from Baseline to Day 28, Day 84 and Day 112 (Cohort 3).

Change in GALT HIV reservoirs will be descriptively summarised on the FAS set.

***11.3.2.3 Change in total viral DNA***

Change in total viral DNA in the reservoir cells from Baseline to Day 28 and Day 56 in HIV-infected subjects (Cohort 1) and from Baseline to Day 28, Day 84 and Day 112 (Cohort 3).

Change in total viral DNA will be descriptively summarised on the FAS set.

***11.3.2.4 Change in inflammatory markers***

Change in inflammatory markers in plasma from Baseline including IL-4, IL-6, IL-8, IL-12, IP-10, G-CSF, IFNg, D-dimer, CRP, sCD14 to Day 28 and Day 56 in subjects enrolled in Cohort 1 & 2 and to Day 28, Day 84 and Day 112 in subjects enrolled in Cohort 3.

Change in inflammatory markers will be descriptively summarised on the FAS set.

***11.3.2.5 Change in immunophenotype***

Change in immunophenotype and assessment of cell-activation markers from Baseline in PBMCs and MMC, using an 11-colours panel, including: CD3, CD8, CD4, CD45RA, CCR7, CD27, CD28, CD38, HLA-DR, PD-1, viability to Day 28 and Day 56 in subjects enrolled in Cohort 1 & 2 and to Day 28, Day 84 and Day 112 in subjects enrolled in Cohort 3.

Change in immunophenotype will be descriptively summarised on the FAS set.

***11.3.2.6 Change in HIV-1 RNA, CD4+ and CD8+ counts***

Change in HIV-1 RNA, CD4+ and CD8+ counts from Baseline to Day 28 and Day 56 in HIV-infected subjects (Cohort 1) and from Baseline to Day 28, Day 84 and Day 112 (Cohort 3).

Change in HIV-1 RNA, CD4+ and CD8+ counts will be descriptively summarised on the FAS set.

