3. INVESTIGATIONAL PLAN

3.1. Study design

3.1.1. Design and methodology

The ABX464-005 study is a Phase Ib, sequential cohort open label trial designed to provide additional safety and compartmental PK data on ABX464.

The study will also generate exploratory immunological and virological data that combined with the compartmental PK data will help further characterize the mechanism of action of ABX464.

The study will enroll both HIV-infected (N=24) and HIV-uninfected (N=12) study subjects in three distinct cohorts:

- Cohort 1: 12 HIV-infected subjects treated with ABX464 150 mg o.d. for 28 days
- Cohort 2: 12 HIV-uninfected subjects treated with ABX464 50 mg o.d. for 28 days
- Cohort 3: 12 HIV-infected subjects treated with ABX464 50 mg o.d. for 84 days

HIV-infected subjects will add the investigational product to their current antiretroviral regimen whereas the HIV-uninfected subjects will only receive the investigational product.

Cohort 1 will consist of 12 HIV infected subjects. After full enrollment and an interim analysis (including PK and immunological markers) of Cohort 1, Cohort 2 and 3 will begin enrollment and will consist of both HIV infected (n=12) and HIV uninfected (n=12) subjects.

Subjects who successfully complete a screening visit (Visit 1) will advance to a Baseline visit (Visit 2; Day 1). During this visit all subjects will undergo a physical examination and have blood and rectal tissue samples collected.

The rectal tissue samples will be collected before initiating oral dosing with the investigational product (150 mg or 50 mg of ABX464).

After receiving the first dose of ABX464, additional blood PK samples will be collected at 0h, 0.5h, 1h, 1.5h, 2h, 4h, 6h and 8 hours.

All subjects will receive the investigational product once daily for 28 days (Cohorts 1 &2) and for 84 days (Cohort 3).

At Day 28 for subjects enrolled in cohort 3 and at the end of the treatment period (End of Rx Visit; Day 28 for Cohorts 1&2 and Day 84 for Cohort 3) subjects will undergo a physical examination and have blood and rectal tissue collected. PK blood samples will be collected at 0h, 0.5h, 1h, 1.5h, 2h, 4h, 6h and 8 hours.

HIV infected subjects will continue with their antiretroviral regimen i.e. there will be no antiretroviral treatment interruption in this study.

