4.2. Eligibility Criteria

4.2.1. Inclusion Criteria

Subjects will be eligible for inclusion in this study only if ALL of the following criteria apply:

- Males aged 18-65 years;
- Subjects with hematological and biochemical laboratory parameters as follows and within 3 weeks of baseline:
 - Hemoglobin > 9.0 g/dL;
 - Absolute neutrophil count \geq 750/mm³;
 - Platelets \geq 100,000/mm³;
 - Total serum creatinine \leq 1.3 x ULN (upper limit of normal);
 - Creatinine clearance $>$ 50 mL/min by the Cockcroft-Gault equation within 60 days of entry;
 - Total serum bilirubin $<$ 1.5 xULN;
 - Alkaline phosphatase, AST (SGOT) and ALT (SGPT) $<$ 1.5 xULN;
 - Serum lipase less than or equal to 2.0 xULN;
- Subjects should be able and willing to comply with study visits and procedures as per protocol;
- Subjects should understand, sign and date the written voluntary informed consent form at the screening visit prior to any protocol-specific procedures being performed;
- Subjects must agree to use in addition to the condom, a second highly effective method (one for the subject and one for the partner) of contraception (defined as per the CTGF Guidance) during the study and for 3 months after end of study or early termination.

For HIV infected Subjects

- Subjects with a positive HIV-1 serology at any time before the study entry.
- Subjects treated for at least 12 months prior to screening with Dolutegravir or Raltegravir combined with either Tenofovir + Emtricitabine (TDF/FTC) or Abacavir + Lamivudine (ABC/3TC);
- Subjects with HIV plasma viral load \leq 50 copies/mL during the 6 months prior to screening with a maximum of 2 blips \leq 1000 copies during this period;
- Subjects' CD4+ T cells count \geq 250 cells per mm³ at any time since diagnosis;
- Subjects with CD4+ T cells count \geq 600 cells per mm³ at screening.

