5.4.4. Viral load and HIV Reservoirs assessment

Regarding HIV-1 viral load, local laboratories will be used as this is done in routine for HIV infected subjects and as

method is standardized so that comparisons between laboratories can be performed.

Viral persistence will be assessed by quantification of total HIV DNA and cell-associated RNA in peripheral blood CD4 T cells and in rectal mucosal leukocytes. In addition, ultrasensitive viral load in plasma will be also assessed.

Experimental design:

Longitudinal analysis of proviral HIV DNA: CD4+ T cells will be isolated by positive selection from total PBMC. Pellets from all time points of each patient (pre- and post-treatment with ABX464) will be lysed, and proviral HIV DNA will be measured by digital droplet PCR (ddPCR, BioRad). Two pairs of primers located in different regions of the viral genome will be used, in order to avoid technical amplification problems due to HIV-1 variability and not due to a real small reservoir. The results will be normalized by the number of cells in each reaction, which will be quantified in parallel through primers targeting the cellular gene RPP30.

Longitudinal analysis of CA-HIV RNA: CD4+ T cells will be isolated by positive selection from total PBMC. Pellets from all time points of each patient (pre- and post-treatment with ABX464) will be lysed, and CA-HIV RNA will be measured by droplet digital PCR (ddPCR, BioRad). Two pairs of primers located in different regions of the viral genome will be used. The results will be normalized by the number of cells in each reaction, which will be quantified in parallel through primers targeting a house-keeping gene.

Longitudinal analysis of plasma VL: ultrasensitive analysis of the VL will be carried out by Single-Copy Assay (SCA) in plasma. Briefly, 10ml of plasma from all time points of each patient (pre- and post-treatment with ABX464) will be concentrated by ultracentrifugation and the determination of the VL will be then performed by the Abbott system. This technique allows detecting down to 1 copy/ml of HIV.

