## 3 Study Design

### 3.1 Overview

The purpose of the ABX464-005 study is to characterize the systemic and mucosal immunological sequelae associated with exposure to ABX464 and to explore selected immunological endpoints, compartmental pharmacokinetics, and pharmacodynamics. The site will screen and enroll 12 HIV-infected subjects who will receive 150 mg ABX464 orally once daily for 28 days (Cohort 1). Following completion of this cohort a further 24 subjects will be enrolled: 12 HIV-uninfected subjects will receive 50 mg ABX464 orally once daily for 28 days (Cohort 2) and 12 HIV-infected subjects (Cohort 3) will receive 50 mg ABX464 orally once daily for 84 days.

Following screening, eligible subjects in both cohorts will undergo a baseline visit during which blood and tissue samples will be collected. All subjects will have additional blood and tissue samples

collected on Day 28 of dosing (and on Day 84 for subjects enrolled in cohort 3) and four weeks after completion of dosing. The HIV infected subjects should be receiving a stable combination antiretroviral regimen for 12 months and be fully virally suppressed (plasma viral load < 50 copies/mL) during the last 6 months prior to enrolment.

Dose limiting toxicity (DLT) is defined as a grade 3 or higher adverse event as defined by the Division of AIDS table for grading the severity of adult and pediatric adverse events (including signs/symptoms, lab toxicities and/or clinical events) considered by the Data Safety Monitoring Board as probably or definitely related to study treatment.

If more than 2 DLTs occur during the treatment period of the first four treated subjects, then the enrolment of additional subjects will be stopped. In addition, in case of a life threatening (grade 4) adverse reaction enrolment and treatment of ongoing subjects will be immediately discontinued. In both cases, enrolment will only be resumed upon the decision of the sponsor if the Data Safety Monitoring Board can conclude that the causality of the event was unrelated or unlikely related to study treatment.

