## 9 Data

## 10 Statistical Methods

### 10.1 General Principles

All statistical methods will be based on the International Conference on Harmonisation (ICH) E9 document "Statistical Principles for Clinical Trials".

Data will be summarised by cohort. A total column showing all patients will be included for baseline and safety summaries. Where appropriate, data will also be summarised by visit with summaries for each visit attended as scheduled and an additional summary for final (last scheduled visit or early withdrawal). The format of the summaries is defined in the shells in a separate document.

All summary tables will be made up of the following three columns:

- Cohort 1: Hiv infected subjects receiving the 150mg dose of ABX464 for 28 days;
- Cohort 2: Hiv uninfected subjects receiving the 50mg dose of ABX464 for 28 days;
- Cohort 3: Hiv infected subjects receiving the 50mg dose of ABX464 for 84 days.

In addition, summary tables for total DNA will be made up with an additional column of cohort 1 and Cohort 3 pooled.

In summary and analysis tables of continuous variables, standard descriptive statistics (N, mean, standard deviation [SD], median, quartiles, minimum, maximum ) will be presented when relevant. 95% confidence Intervals (CI) will be presented in the statistical analysis outputs as appropriate. For PK summaries, arithmetic mean (AM), geometric mean (GM) and coefficient of variation (%CV) will be used to summarise the data. The minimum and maximum statistics will be presented in summary tables to the same number of significant figures as the original data. The mean/AM, median, GM, CI, SD and will be presented to one more significant than the original data.

For numeric data which includes non-numeric values (e.g. PK data reported as BLQ or lab results reported as < 10 or >100) the following principles will be applied when summarising the data:

- BLQ will be replaced with a value that is ½ of the lower limit of quantification (LLQ)
- Results reported as < x will be treated in the same way as BLQ with LLQ=x
- Otherwise AM, GM, SD, CI and %CV will not be calculated
- Whenever meaningful, minimum, median and maximum will be presented based on the reported data (e.g. minimum = <10, median = 20, maximum = >100)

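### Change in HIV-1 RNA is exactly zero for any subject below the routine assay's limit at both visits, and the single-copy assay that the protocol collects has no analysis in the SAP

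*SAP*

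**What the plan says.** SAP 11.3.2.6 covers change in HIV-1 RNA from Baseline to Days 28 and 56 (Cohort 1) and to Days 28, 84 and 112 (Cohort 3). The whole analysis is one sentence, "Change in HIV-1 RNA, CD4+ and CD8+ counts will be descriptively summarised on the FAS set", and it names no assay.

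SAP 10.1 sets a general rule for numeric data that contain non-numeric results. A value below the limit of quantification is replaced by half that limit, and "Results reported as < x will be treated in the same way as BLQ with LLQ=x". HIV-1 RNA is not exempted. For the order statistics the same section adds: "Whenever meaningful, minimum, median and maximum will be presented based on the reported data".

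On the population, SAP 3.1 asks that HIV-infected subjects "be fully virally suppressed (plasma viral load < 50 copies/mL) during the last 6 months prior to enrolment". Protocol 4.2.1 words this as at most 50 "copies/mL during the 6 months prior to screening with a maximum of 2 blips" of up to 1000 copies. Protocol 3.1.1 adds that "there will be no antiretroviral treatment interruption in this study".

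Protocol 5.4.4 describes two plasma measurements: a routine viral load at local laboratories, with no limit given, and an ultrasensitive single-copy assay at all time points. Of the second it says: "This technique allows detecting down to 1 copy/ml of HIV". The flow chart in Protocol 5.1 lists them on separate rows. The SAP does not mention the single-copy assay in its endpoints (4.2), interim content (8) or analyses (11.3).

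**The concern.** Subjects are selected for having little or no measurable virus and continue the treatment that keeps it so. Their routine results will mostly be reported as below a limit. Under the half-limit rule such results become a constant, and a constant minus itself is zero whatever happened below the limit.

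Two things are at stake. First, a fall in residual viraemia within the suppressed range cannot be seen in this endpoint, and the assay that could show it has no planned summary. Second, a table of zeros with no spread can be read as a precise finding of no change, when it comes from the substitution rule and from a cohort of only 12.

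**Working it through.** The plan gives no effect size, SD or assay limit for HIV-1 RNA, so there is no figure of its own to reproduce.

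**Inputs**
- From the documents: half-limit rule (SAP 10.1); 12 HIV-infected subjects in each of Cohorts 1 and 3, so 24; single-copy limit 1 copy/mL (Protocol 5.4.4).
- Assumed: routine limit L = 20, 40 or 50 copies/mL. The 50 in the documents is an eligibility threshold, not a stated assay limit.

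**1. The rule applied.** Let f(v) = L/2 if v < L, otherwise v. Change = f(post) − f(baseline). When both values are below L this is L/2 − L/2 = 0, on the raw and on the log10 scale. The largest hidden fall to 1 copy/mL starts at L − 1:

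| L | value used | recorded change | hidden fall, copies | hidden fall, log10 |
|---|---|---|---|---|
| 20 | 10 | 0 | 19 − 1 = 18 | log10(19) = 1.28 |
| 40 | 20 | 0 | 39 − 1 = 38 | log10(39) = 1.59 |
| 50 | 25 | 0 | 49 − 1 = 48 | log10(49) = 1.69 |

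**2. Where the change is not zero.** A rise from 10 to 200 copies/mL is recorded as 200 − L/2 = +190, +180 or +175 for L = 20, 40, 50. With L = 20, a fall from 30 to 5 is recorded as 10 − 30 = −20.

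**3. How many pairs are zero.** Let q be the chance of a quantifiable result at a visit, assumed independent between visits. The share of pairs below the limit at both visits is (1 − q)².

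| q (assumed) | share | expected of 12 | expected of 24 | P(at least 7 of 12 zero) |
|---|---|---|---|---|
| 0 | 1.00 | 12 | 24 | 1.00 |
| 5% | 0.902 | 10.8 | 21.7 | 1.00 |
| 10% | 0.81 | 9.7 | 19.4 | 0.985 |
| 20% | 0.64 | 7.7 | 15.4 | 0.765 |
| 30% | 0.49 | 5.9 | 11.8 | 0.36 |

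Seven or more zeros among 12 guarantee a median change of 0. Zeros are the majority as long as q is below 1 − √0.5 = 0.29.

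**4. Apparent precision when nobody rebounds.** If all 12 pairs are below the limit, the mean is 0, the SD is 0, and any interval built on that SD is [0, 0]. For the count at or above 50 copies/mL, the exact two-sided 95% upper limit for 0/n is 1 − 0.025^(1/n):
- n = 12: 26.5%
- n = 24: 14.2%

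**5. Mean change when one subject rebounds (L = 50).** A rise to 1000 copies/mL gives 975/12 = +81 copies, with a median of 0. A rise to 200 gives 175/12 = +14.6 copies, with SD 175/√12 = 50.5. Neither mean tells the reader that one subject in 12 lost control.

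**6. Routine versus single-copy assay.** A simulation of a true 50% fall (−0.301 log10) assumed a baseline log10 SD of 0.5, a change SD of 0.15, and the half-limit rule for both assays.

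| assumed baseline median (copies/mL) | routine mean change, L = 20 / 40 / 50 | routine exact zeros | single-copy mean change | single-copy exact zeros |
|---|---|---|---|---|
| 1 | −0.002 / 0.000 / 0.000 | 99.5% to 100% | −0.174 | 50% |
| 3 | −0.018 / −0.005 / −0.003 | 95% to 99.3% | −0.274 | 17% |
| 10 | −0.097 / −0.040 / −0.029 | 73% to 92% | −0.304 | 2% |

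The routine assay recovers at most about a third of the fall (0.097/0.301 = 0.32). The single-copy assay recovers most of it, except at a median of 1 copy/mL, where half-limit substitution again pulls the estimate towards zero.

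**The case against.** The defence has several fair points.

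- **Rebound is visible.** The secondary objective concerns control of the viral load. In suppressed subjects on continued treatment, loss of control means rebound, and the routine assay records it. A reader might infer that the objective goes unanswered or that every subject's change is zero. The documents support neither reading: zero holds only for pairs below the limit at both visits, and eligibility allows earlier blips, so quantifiable values can occur.
- **The limit is unknown.** With a limit of 20, some movement under 50 copies/mL would show. This is why a range is given above.
- **Reported values are kept for minimum, median and maximum.** This helps the by-visit tables, and the listings show the raw results. It does not repair a change score, because one below-limit result minus another has no reported value.
- **The single-copy assay is not in the protocol's endpoint list** (Protocol 5.2), and Protocol 3.1.1 calls the virological data exploratory. So the SAP follows the protocol's endpoints. SAP 11.3.2.6 names no assay, and the table shells are in a separate document. It is therefore an inference that HIV-1 RNA means the routine assay, although the separate flow-chart rows favour it.
- **The endpoint is descriptive.** There is no hypothesis test, and the reservoir has its own DNA and rectal-tissue endpoints.

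A reader might also fear a false fall if the reporting limit changed between visits. Nothing supports that: there is one site, and Protocol 5.4.4 calls the method standardised.

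These points narrow the concern. They do not supply a summary that can show a fall within the suppressed range, or one that conveys the uncertainty when no rebound is seen.

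**Conclusion.** The point holds in a limited form. Under SAP 10.1, change in HIV-1 RNA is exactly zero for every subject below the routine assay's limit at both visits. The endpoint can therefore show loss of control but almost no reduction. The hidden fall to 1 copy/mL is up to about 1.3 to 1.7 log10 for assumed limits of 20 to 50 copies/mL. If 5% to 10% of results per visit are quantifiable (assumed), about 10 or 11 of 12 changes per cohort are exact zeros. If there is no rebound, the planned statistics overstate precision: [0, 0] for the mean against an exact upper limit of 26.5% (12 subjects) or 14.2% (24 subjects) for the proportion at or above 50 copies/mL. The single-copy assay has no stated analysis or below-limit rule of its own in the SAP.

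This rests on the routine assay supplying HIV-1 RNA and on most subjects staying suppressed. CD4+ and CD8+ counts are unaffected. It concerns one descriptive secondary endpoint and does not touch the primary PK analysis, but it should be corrected because correction is cheap.

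**What to change.** In SAP 11.3.2.6:

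1. Name the routine assay and state its limit.
2. Make the main summary the number and percent at or above 50 copies/mL at each visit, by cohort, with an exact 95% CI, instead of relying on mean change of half-limit values.
3. Add a descriptive summary of the single-copy assay, labelled exploratory: the proportion detectable by visit, and log10 change with values below its limit treated as censored rather than halved.

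The cost is SAP wording and one or two tables. No new samples are needed, since the flow chart already schedules the single-copy assay. The exploratory label is necessary because the protocol's endpoint list does not name that assay. SAP 8 reports that a Cohort 1 interim analysis including HIV-1 RNA has already been produced, so the revision should state that it postdates those data. Protocol 9 requires SAP amendments to be justified and signed before final database lock.

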***11.3.2.7 Change of rectal microbiota***

Change of rectal microbiota using taxonomic markers from Baseline to Day 28 and Day 56 in subjects enrolled in Cohort 1 & 2 and to Day 28, Day 84 and Day 112 in subjects enrolled in Cohort 3.

Change of rectal microbiota will be descriptively summarised on the FAS set.

***11.3.2.8 Change in the transcriptome & proteome***

Change in the transcriptome & proteome from Baseline to Day 28 and Day 56 in subjects enrolled in Cohort 1 & 2 and to Day 28, Day 84 and Day 112 in subjects enrolled in Cohort 3.

Change in the transcriptome & proteome will be descriptively summarised on the FAS set.

## 11.4 Safety Analysis

In addition to the analysis of the secondary safety endpoint the following safety assessments will also be presented.

### 11.4.1 Adverse Events

All adverse events (AE) will be classified using the version of the MedDRA coding dictionary.

Events will be classified as treatment-emergent if they started or increased in severity on or after the first date and time of medication dosing at Day 1 and up to End of Rx, or withdrawal date if the

patient discontinues before End of Rx. If an event start date is partial, then the start day, month, year or stop date will be used to determine if the event is treatment-emergent. If the classification of the AE cannot be determined from the data available, then the event will be considered treatment-emergent.

Any adverse event which occurs after End of Rx will be classified as post-treatment-emergent.

An overall summary table will be presented using the safety set for adverse events occurring from baseline to the end of the study in the following categories:

- Any adverse event;
- Any treatment-emergent adverse event (TEAE);
- Any post-treatment-emergent adverse event;
- Any serious adverse event;
- Any severe adverse event (Common Toxicity Criteria [CTC] grade 3 or 4);
- Death

TEAEs will be further classified and summarised as follows:

**Severe TEAEs:** Severity classified as 'Grade 3', 'Grade 4' or missing.

**Serious TEAEs:** Seriousness classified as 'yes' or missing.

**Drug-related TEAEs:** Relationship to study drug classified as 'yes' or missing.

**Serious drug-related TEAEs:** Both serious and drug-related, as specified above.

**TEAEs leading to study drug discontinuation:** Action taken classified as 'permanent discontinuation'.

Summaries by system organ class (SOC) and preferred term (PT) will also be presented for treatment-emergent events. Similar tables will be presented for each of the classifications of treatment-emergent events above.

A summary of the mean duration (days) of treatment-emergent events will also be presented by SOC and PT, along with the number of events. Duration of an event is calculated as (stop date of event - start date of event) + 1. If an AE is ongoing then use the end of study date (or last known visit date for early termination) as the stop date.

All AE summary tables, unless otherwise specified, will show the number (%) of patients having at least one event and the number of events in each treatment group and overall. Note: If a patient has multiple AEs with the same preferred term, these will be summarised once within the count for N (%) of patients, but each event will be counted within the number of reports E of each AE. Changes in severity of the same AE (if collected) will be counted only once within the number of reports E of each AE.

All adverse events recorded on the CRF will be listed by SOC and PT within the data listings.

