9.3. Safety Analyses

Adverse events will be coded using the standard dictionary (MedDRA) down to the lower level term (LLT).

An overall summary table will be presented: any adverse event, any treatment emergent adverse event (TEAE), any serious adverse event (SAE), death, any grade 3 or higher adverse events from baseline to EoS.

Two periods will be defined for TEAE:

- Any adverse event which occurs or worsens from first dosing to Day 28;
- Any adverse event which occurs after Day 28.

Adverse events will be described by primary system organ class and preferred term. Numbers and percentage of subjects, and number of occurrence of adverse event will be presented for:

- TEAE;
- Serious TEAE;
- TEAE leading to drug discontinuation;
- TEAE of grade 3 or 4;
- TEAE for which relationship with the study drug is recorded as possible or probable.

The assessment of safety will be based on the frequency of adverse events (with and without regard to causality) graded according to the Division of AIDS table for grading the severity of adult and pediatric adverse events (version 2.0, November 2014) and also, the review of individual values for clinical laboratory data, vital signs and ECG focusing on the detection of abnormal values and PCSAs [potentially clinically significant abnormalities (PCSA) determined upon investigator considerations].

Adverse events will be tabulated (counts and percents) by group. All adverse events will be listed and the data will be tabulated by body system/organ class. Adverse event tabulations will include all treatment emergent adverse events, which will be further classified by severity, and relationship to treatment and dose level.

Clinical laboratory parameters, vital signs, ECG will be summarized by using descriptive statistics (n, mean, SD, SEM, median, minimum and maximum). Number of subjects with at least one abnormal values will be tabulated (counts and percents) for each parameter in summary shift tables, by group and dose.

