#### 4.4 Safety endpoint

Analysis of safety will be performed on the safety data set consisting in all subjects who received at least one dose of ABX464 in the study. The assessment of safety will be based on the frequency of adverse events (with and without regard to causality) graded according to the Division of AIDS table for grading the severity of adult and pediatric adverse events (Version 2.0 November 2014) and also, the review of individual values for clinical laboratory data, vital signs and ECG focusing on the detection of abnormal values and PCSAs [potentially clinically significant abnormalities (PCSA) determined upon investigator considerations].

Adverse events will be tabulated (counts and percents) by group and dose. All adverse events will be listed and the data will be tabulated by body system/organ class. Adverse event tabulations will include all treatment emergent adverse events, which will be further classified by severity, and relationship to treatment and dose level.

Clinical laboratory parameters, vital signs, ECG will be summarized by using descriptive statistics (n, mean, SD, SEM, median, minimum and maximum). Number of subjects with at least one abnormal values will be tabulated (counts and percents) for each parameter in summary shift tables, by group and dose.

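### Protocol 9.3 counts events after Day 28 as TEAEs but SAP 11.4.1 ends TEAEs at End of Rx, so the first-listed secondary endpoint has two different counts

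*SAP*

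**What the plan says.** **Protocol 9.3** defines two periods and labels both as TEAE periods. The first is "Any adverse event which occurs or worsens from first dosing to Day 28"; the second is everything occurring after Day 28, with no upper limit. It then asks for displays by system organ class (SOC) and preferred term (PT) of all TEAEs, serious TEAEs, TEAEs leading to discontinuation, grade 3-4 TEAEs and related TEAEs. Follow-up events belong in these displays.

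**SAP 11.4.1** classes an event as treatment-emergent if it starts or worsens "on or after the first date and time of medication dosing at Day 1 and up to End of Rx", or up to the withdrawal date for a subject who stops early. It adds: "Any adverse event which occurs after End of Rx will be classified as post-treatment-emergent". The detailed tables follow that class: "Summaries by system organ class (SOC) and preferred term (PT) will also be presented for treatment-emergent events", and "Similar tables will be presented for each of the classifications of treatment-emergent events above". Those classifications (severe, serious, drug-related, leading to discontinuation) are defined for TEAEs.

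Follow-up events do appear in three places in the SAP:

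- The overall summary in 11.4.1 runs to the end of the study. It has one row for post-treatment-emergent events, and its any-AE, serious, grade 3-4 and death rows include them.
- Section 11.4.1 also states: "All adverse events recorded on the CRF will be listed by SOC and PT within the data listings".
- Section 4.4 bases safety on AE frequency, both ignoring causality and taking it into account, and says: "All adverse events will be listed and the data will be tabulated by body system/organ class". It continues: "Adverse event tabulations will include all treatment emergent adverse events, which will be further classified by severity, and relationship to treatment and dose level".

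**The concern.** Number and grade of TEAEs is the first-listed secondary endpoint in both documents (protocol 5.2, SAP 4.2). Section 9 of the protocol presents the SAP as a more detailed version of the protocol's analysis. Here the SAP changes the definition and neither records nor explains the change. Two analysts working from the two documents would report different TEAE and related-TEAE counts from the same database.

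The affected period matters for safety. Protocol 8.4 collects AEs until 4 weeks after the last dose, and protocol 8.5 has the investigator assess causality for every AE. Protocol 5.4.8 gives the main metabolite a half-life of 90 to 110 h, so exposure continues past the last dose. An investigator could reasonably attribute an event at the 1-week follow-up visit to the drug. Under the SAP text that attribution would be readable only from a listing.

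**Working it through.** The plan states no figure on this point. The check sets the definitions side by side and then sizes the period on which they differ.

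**1. Illustrative events under each document**

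| Event | Protocol 9.3 | SAP 11.4.1 |
|---|---|---|
| Cohort 1 or 2 completer, new event Day 35, judged related | TEAE; meant for the SOC/PT and related-TEAE displays | Post-treatment; overview rows and listing only |
| Cohort 3, new event Day 60 on drug | TEAE (second period) | TEAE |
| Cohort 3, new event Day 91 | TEAE (second period) | Post-treatment |
| Cohort 1, last dose Day 10, new event Day 20 | TEAE (first period) | Depends on what the withdrawal date means |

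In the last row, suppose the withdrawal date is the last dose. The TEAE window has then closed, and if End of Rx means the Day 28 visit, the post-treatment class has not yet opened. If instead it is the End of Study visit, which protocol 7.3 places within two weeks of the last dose (up to Day 10 + 14 = 24), the event is a TEAE.

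**2. Nominal days outside the SAP window**

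Inputs: treatment of 28 days (Cohorts 1 and 2) or 84 days (Cohort 3), follow-up of 28 days (protocol 3.2), and 12 subjects per cohort.

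- Cohorts 1 and 2: 28 / (28 + 28) = 28/56 = 50%.
- Cohort 3: 28 / (84 + 28) = 28/112 = 25%.
- All 36 subjects, if all complete: follow-up 36 × 28 = 1008 days; on treatment 24 × 28 + 12 × 84 = 1680 days; 1008/2688 = 37.5%.

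**3. Metabolite remaining after the last dose**

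Fraction = 2^(−hours / half-life), with half-life 90 and 110 h (protocol 5.4.8). Mono-exponential decay is assumed.

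| Days after last dose | Hours | 90 h | 110 h |
|---|---|---|---|
| 7 | 168 | 27% | 35% |
| 14 | 336 | 8% | 12% |
| 28 | 672 | 0.6% | 1.4% |

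Five half-lives are 5 × 90/24 = 18.8 to 5 × 110/24 = 22.9 days. The parent drug has a half-life of 1 to 2 h, so it contributes essentially nothing in follow-up.

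**4. The protocol's own rule also needs repair**

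- For Cohort 3 its second period joins 84 − 28 = 56 on-drug days to 112 − 84 = 28 off-drug days.
- Its related-TEAE display needs causality recorded as possible or probable, but section 8.5 records only YES or NO.
- Its second period mentions events that occur, but not events that worsen.

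**The case against.** The strongest reply is that little is lost. Serious, grade 3-4 and fatal follow-up events are counted in the overview, every event is listed by SOC and PT, and with 12 subjects per cohort a listing can be read directly. This stands as far as it goes: it limits the gap to tables and makes the repair a modest one.

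A reader might infer that a related follow-up event will appear in no relatedness summary at all. The documents do not support that. SAP 10.1 and 11 leave table layouts to shells in a separate document, and SAP 4.4 promises AE frequency with causality taken into account. What can be said is that the SAP text specifies no PT-level or drug-related table for these events; section 4.4 names the severity and relationship split for treatment-emergent events.

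A reader might also infer that the SAP cut fails for Cohort 3. It does not: End of Rx is Day 84 there, so on-drug and off-drug time stay apart for completers. The SAP does lose the protocol's common Day 1-28 window, so 84-day and 28-day crude percentages stand side by side. That affects comparability only. The cohorts are not randomised and differ by design in dose, HIV status or duration.

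Finally, the documents do not attribute adverse events to the metabolite, and little of it remains by the end of follow-up. The exposure argument is strongest in the first two weeks.

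**Conclusion.** The conflict is real and should be resolved before the analysis. For the first-listed secondary endpoint, the TEAE and related-TEAE counts depend on which document is followed. The difference concerns events in 28 of 56 nominal days in Cohorts 1 and 2 and 28 of 112 in Cohort 3. These are shares of calendar time: the documents do not show how many events would move, and a reader should not take 50% or 25% as a share of events.

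The conclusion on definitions rests on the two texts alone. The conclusion on missing tables is limited to the SAP text, because the shells were not available. The exposure figures assume mono-exponential decay from the last dose at the half-lives the protocol states. The early-stopper ambiguity follows from the SAP leaving the withdrawal date undefined. Nothing here shows that safety data would be lost.

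**What to change.** - **Definition, in both documents.** A TEAE is an event with onset or worsening from first dose through the 4-week post-dose AE collection window. Split it into on-treatment and post-treatment at each subject's own last dose. This removes the early-stopper ambiguity and the mixing of on-drug and off-drug days in the protocol's second period for Cohort 3.
- **Tables.** Keep the on-treatment SOC/PT tables as planned. Add one SOC/PT table for the post-treatment part showing grade and drug-relatedness.
- **Relatedness.** In protocol 9.3, replace the possible-or-probable category with the YES/NO answer recorded under protocol 8.5.
- **Optional.** An on-treatment Day 1-28 table for all three cohorts, for comparability.

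The cost is wording in two documents and a few tables from data already collected. Some late unrelated events will enter the TEAE totals; the split keeps them visible. Early stoppers have their End of Study visit within two weeks of the last dose (protocol 7.3), so a footnote should say that their post-treatment part may cover less than 4 weeks.
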